## **11 STATISTICAL METHODS**

### **11.1 Sample Size Estimation**

Sample size is not formally determined a priori, as the aim of this randomised pilot study is to determine feasibility for a future definitive randomised trial. However, we deem a sample size of at least 50 participants per arm as reasonable for allowing estimation of key feasibility parameters.

### **11.2 Population to be analysed**

The study sample will be analysed via the intention-to-treat principle. Therefore, all randomised participants will be included analysis, regardless of whether they received and/or adhere to their allocated trial drug.

---

### 11.2.1 Handling of missing data

All qualitative data will be analysed according to the intention-to-treat principle. No missing data will be imputed. There are no data substitutions for adverse events or adherence.

### 11.3 Methods of analysis

The two secondary aims of this feasibility study will be addressed statistically. For the first secondary aim, diagnosis of CRPS will be ascertained in the form of time-to-event data, and rate ratios will be calculated using univariate Cox proportional hazards regression to directly compare diagnosis rates between the treatment and control groups.

Given the small sample size of this feasibility study, we anticipate randomization may inadequately balance the baseline characteristics of participants in the two treatment groups (e.g. age, trauma vs elective surgery). If necessary, a secondary set of analyses will be performed to adjust for baseline characteristics found to be imbalanced between groups to the extent of a 0.25 standard deviation difference in means (quantitative measures) or an odds ratio of 1.5 (binary measures). These analyses will be conducted using multivariate Cox proportional hazards regression models.

In the survival analyses, loss to follow-up will be considered a censoring event. This equates to an assumption that data is missing at random given the participant's treatment group and the timing of their loss to follow-up. The adequacy of this assumption will be checked in sensitivity analyses that will include both a multiple imputation by chained equations (MICE) approach and adjustment for baseline covariates predictive of propensity for dropout.

A sensitivity analysis will repeat the proportional hazards regression to compare rates of CRPS as diagnosed by the presence of individual Budapest criteria, rather than 3 out of 4 patient-reported symptoms or 2 out of 4 clinician-observed symptoms as required for formal CRPS diagnosis.

For the second secondary aim, the incidence risk of CRPS 6 months post surgery for lower limb extremity trauma patients will be reported as a proportion of the study sample.

Adverse events will be coded as per the Medical Dictionary for Regulatory Activities. Adverse events will be calculated at each visit, and patients may have more than one adverse event. Assessment of severity, frequency and relationship of adverse events to trial intervention will be presented by System Organ Class and information such as start date, stop date, severity, relationship expectedness, outcome and duration will be recorded. Adverse events leading to premature discontinuation from the trial intervention and serious treatment-emergent adverse events will be presented in a table.

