## 6 RANDOMISATION AND BLINDING

An investigator not directly involved in the analysis of the trial results will prepare the randomisation schedule using block randomisation to maintain balance between treatment arms. This will be Associate [name] as she will not be directly involved in the analysis. The schedule will be provided to the pharmacist and sealed envelopes containing the treatment allocation of each randomisation code will be provided to the investigator in case of emergency.

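### The secondary adjusted Cox model takes its covariates from observed imbalance (0.25 SD or odds ratio 1.5), thresholds that at 50 per arm lie close to chance variation

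*Protocol*

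**What the plan says.** Section 11.3 makes the unadjusted model the main comparison of CRPS diagnosis between arms: "rate ratios will be calculated using univariate Cox proportional hazards regression". It then gives the reason for an adjusted analysis: "we anticipate randomization may inadequately balance the baseline characteristics of participants in the two treatment groups (e.g. age, trauma vs elective surgery", named as examples. The adjusted analysis is conditional: "If necessary, a secondary set of analyses will be performed". Its covariates are fixed by a numerical rule, which is to "adjust for baseline characteristics found to be imbalanced between groups to the extent of a 0.25 standard deviation difference in means" for quantitative measures, or by "an odds ratio of 1.5 (binary measures" for the others. No list of candidate covariates is given, and expected relation to CRPS plays no part in the choice.

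On size, section 11.1 states that "we deem a sample size of at least 50 participants per arm as reasonable". On allocation, section 6 specifies a schedule "using block randomisation to maintain balance between treatment arms" and names no stratification factor.

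Baseline variables appear in two places. The outcome table in section 3.2 has seven (age, gender, mechanism of injury, workers' compensation, smoking, diabetes, prior CRPS). Section 7.4 has an overlapping but different list that adds mental health history, compensable status, surgery type and surgical site.

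**The concern.** Adjustment helps when a covariate predicts outcome. A rule based on observed imbalance selects on something else. In a properly randomised trial every baseline difference is a chance difference, so such a rule is useful only if its thresholds lie well outside chance variation. Here they do not.

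Three things follow.

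- The make-up of the adjusted model is close to a lottery. The rule is most easily met by rare factors, where one patient decides: 2 versus 1 affected patients out of 50 gives (2/48)/(1/49) = 2.04, which is over the threshold.
- Age or surgery type, the two factors the plan itself worries about, is left out whenever it falls just under its threshold.
- Several flagged covariates may enter a Cox model that has few CRPS events to support them.

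The protocol itself fixes this rule, so it is not a matter left open for a later analysis plan.

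**Working it through.** The protocol states no probability for its triggers, and section 11.1 says that "Sample size is not formally determined a priori", so there is no figure of the plan's own to reproduce. The inputs from the protocol are n = 50 per arm (section 11.1) and the two thresholds (section 11.3). Prevalences and CRPS risk are assumptions. The odds-ratio rule is read as 1.5 or more, or 1/1.5 or less, because the reference category is arbitrary.

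**Quantitative covariate.** The standard error of the standardised difference is sqrt(2/50) = 0.20. The threshold is 0.25/0.20 = 1.25 standard errors, so P(flag) = 2 × (1 − Φ(1.25)) = 21.1%.

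**Binary covariate.** The standard error of the log odds ratio is about sqrt(2/(50·p·(1−p))). At p = 0.5 this is 0.40 against ln 1.5 = 0.405, so the threshold is about one standard error. At p = 0.05 it is 0.918, so the threshold is 0.44 standard errors. Exact enumeration of two independent Bin(50, p) counts gives:

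| Prevalence | P(flag by chance) |
|---|---|
| 50% | 31.2% |
| 30% | 35.7% |
| 20% | 42.6% |
| 10% | 56.9% |
| 5% | 73.0% |

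The 5% row counts tables in which one arm has no affected patient (odds ratio zero or infinite). Without those tables it is 58.8%.

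**The two named factors** (independent, trauma/elective at an assumed 50/50 split):

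- At least one flagged: 1 − (1 − 0.211)(1 − 0.312) = 45.7%.
- Neither flagged: 54.3%.
- Both flagged, so that the model adjusts for both: 0.211 × 0.312 = 6.6%.

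**Seven covariates** (age plus six binaries, independent):

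- All six at 50% prevalence, close to the least trigger-prone case for a common factor: 1 − 0.789 × 0.688^6 = 91.6%, with 0.211 + 6 × 0.312 = 2.1 flagged on average.
- Assumed prevalences of 55, 3, 25, 10, 50 and 35%, with flag probabilities 0.329, 0.742, 0.388, 0.569, 0.312 and 0.349: at least one flag in 98.4% of trials, 2.9 flagged on average. Without empty-arm tables this is 96.2% and 2.55.
- If the odds ratio is read in one direction only, each binary probability halves. The two figures fall to 71.5% and 83.4%.
- Correlation hardly matters. In a simulation of nine covariates with a latent correlation of 0.5, at least one flag occurred in 99.3% of trials, against 99.5% with independence.

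**Events.** Assume a control risk of 5% to 30% (section 2.2 cites up to 30% after tibial shaft fracture; the lower end is an assumption) and a risk ratio of 0.5. Expected events run from 50 × 0.05 + 50 × 0.025 = 3.75 to 50 × 0.30 + 50 × 0.15 = 22.5. Three flagged covariates plus treatment make four parameters, or 0.9 to 5.6 events per parameter. Treatment plus two fixed covariates make three, or 1.25 to 7.5.

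**The case against.** The case for leaving the text alone has real force.

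- **The consequence is small.** The unadjusted model is the main comparison and is reported regardless. CRPS is a secondary aim, the primary objective is feasibility, and nothing in the protocol ties the adjusted hazard ratio to a decision about the larger trial. This stands, and it limits the weight of the point.
- **The rule is numerical, set in advance and blind to outcome.** A reader might infer that it lets the analyst choose a favourable result. The protocol does not support that: selection acts on baseline differences, not on the effect estimate. What remains open is which variables are examined, since sections 3.2 and 7.4 list different ones.
- **A reader might infer that chance triggers the rule almost always.** That holds only over the whole collected baseline set, and on assumed prevalences. It is not true of a single covariate or of the two named factors together (46%). The rule also covers only quantitative and binary measures, whereas section 7.4 collects compensable status, surgery type and surgical site in several categories, so treating these as binary is a further assumption.
- **A reader might infer that randomisation is faulty because the blocks are not stratified by surgery type.** It is not. Unstratified blocks are valid, and chance imbalance is compatible with sound randomisation. Section 2.2 calls trauma the commonest precipitating event, but it offers no comparison of trauma with elective patients among those operated on. The protocol does not establish surgery type as the main risk factor.
- **A fixed model is not rich in events either.** The gain from four parameters to three is modest. This stands too: the case for a fixed model rests on its covariates being chosen for a reason and known in advance, not on precision.

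**Conclusion.** The point holds in limited form. The imbalance rule in section 11.3 is a poor way to choose covariates, because at 50 per arm its thresholds lie at about 0.4 to 1.25 standard errors of chance variation. It filters little, ignores expected relation to CRPS, and adjusts for both named factors in only about 7% of trials.

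The per-covariate 21% depends only on the sample size and the threshold. The binary figures depend also on prevalence, on the two-way reading of the odds ratio and, for rare factors, on how empty arms are counted. The 92% to 98% for seven covariates rests on all of these, and the one-way reading lowers it to about 72% to 83%. The direction of the conclusion is the same throughout.

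The correction is worth making because it costs little and because this protocol is meant to inform a larger trial. It does not affect the feasibility conclusions or the unadjusted comparison.

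**What to change.** In section 11.3:

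1. Delete the 0.25 SD and odds-ratio 1.5 trigger.
2. Keep the unadjusted Cox model as the main comparison.
3. Pre-specify one secondary adjusted Cox model with treatment, surgery type (trauma/elective) and age, fitted whatever the observed balance and labelled exploratory. State where the category for other surgery in section 7.4 is placed.
4. Use a small-event method such as Firth penalisation if events are few, and state in advance the event count at which it applies (or use it throughout).
5. Report the remaining baseline variables descriptively by arm, with no imbalance test or trigger.

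The cost is a few sentences. The variables are already collected, and the change can be made before the codes are released under section 6.3.2. The downside is that with very few events even this model will be imprecise.

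Stratifying the blocks by trauma/elective is optional and not part of the correction. It would restrict imbalance on that factor to incomplete blocks. However, section 5.2.4 stocks five sites in advance, so two series would mean up to ten stocks, more part-filled blocks and more chance of dispensing from the wrong series.

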## 2. INTRODUCTION AND BACKGROUND

### 2.1. Trial rationale and aim

We aim to perform a feasibility study, with the potential for a larger trial in the future.

Primary objective – to determine if the proposed protocol is feasible with regards to:

- Recruitment capability
- Data collection procedure
- Suitability of intervention
- Resource availability
- Participant response

Secondary objective:

- to determine if vitamin C prevents CRPS in patients with lower limb extremity trauma in a dose-response manner
- to determine the incidence risk of CRPS in lower limb extremity trauma and elective surgery

The role of vitamin C and the prevention of CRPS has been demonstrated in upper limb trauma(2) but not clearly proven in lower limb trauma and elective surgery. A randomised controlled trial is yet to be published on this important topic, but several quasi-randomised trials have demonstrated the efficacy and safety of vitamin C in CRPS prevention(3)(4).

It is the experience of the senior author that complex regional pain syndrome was a common complication of lower extremity trauma and any means to prevent this debilitating disease was worth investigating to see if a simple, cheap intervention such as vitamin C, which has been demonstrated to prevent CRPS in upper limb trauma, would also be effective in lower limb trauma.

As a trial of this nature has not been conducted before, a feasibility trial is appropriate to assess the effectiveness of the protocol.

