#### **3.1.2 Secondary objectives**

Secondary objective:

1. to determine if vitamin C prevents CRPS in patients with lower limb extremity trauma in a dose-response manner

2. to determine the incidence of CRPS in lower limb extremity trauma.
3. To determine the demographics and characteristics of patients who develop CRPS of the lower limb

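### The 6-month CRPS incidence is defined for trauma patients but divided by the whole mixed sample, and the protocol does not settle which population the incidence objective covers

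*Protocol*

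**What the plan says.** Section 11.3 gives the estimator for the second secondary aim in one sentence: the "incidence risk of CRPS 6 months post surgery for lower limb extremity trauma patients will be reported as a proportion of the study sample". Section 11.2 defines who is in that sample: "The study sample will be analysed via the intention-to-treat principle", and "all randomised participants will be included analysis, regardless of whether they received and/or adhere to their allocated trial drug". Sections 4.3 and 4.4.1 enrol elective and emergency foot and ankle surgery together, and no planned trauma share is given.

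The objective is stated in two ways. Section 2.1 has "to determine the incidence risk of CRPS in lower limb extremity trauma and elective surgery", and the synopsis also names both trauma and elective surgery. Section 3.1.2 has only "to determine the incidence of CRPS in lower limb extremity trauma", and the objectives table in 3.2 follows it.

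On incomplete follow-up, 11.2.1 says "No missing data will be imputed". Section 11.3 says "In the survival analyses, loss to follow-up will be considered a censoring event" and plans a "multiple imputation by chained equations (MICE) approach" as a sensitivity analysis. Neither the censoring rule nor the sensitivity analysis is extended to the incidence proportion. No incidence by arm is planned.

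**The concern.** A risk for trauma patients needs trauma patients in both numerator and denominator. The sentence in 11.3 names trauma patients for the risk and the whole sample for the denominator. Followed as written, it understates the trauma risk by a factor that depends only on case mix, which has nothing to do with CRPS. Because the objective itself changes between sections, a reader cannot tell from the protocol which population the published figure would describe.

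Two related gaps affect the same figure. The section handles CRPS as time-to-event data with censoring for the treatment comparison, but switches to a plain proportion for incidence without saying what happens to patients whose 6-month status is unknown. It also pools a placebo arm with an arm given a treatment that the first secondary objective supposes may prevent the condition.

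What is at stake is the interpretability of one of the two secondary aims that 11.3 says will be addressed statistically.

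**Working it through.** **No planning figure to reproduce.** Section 11.1 sets at least 50 per arm without a formal calculation. 2 × 50 = 100 agrees with the approximate 100 in section 4.7. The protocol assumes no incidence, precision or dropout rate. The only lower-limb CRPS rate it cites is 30% after tibial shaft fracture (section 2.2), and that is not used for planning.

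**Inputs.** All are assumptions except the 30%: p = true untreated risk in trauma patients; t = trauma share of the sample; d = share lost before a diagnosis is recorded; RR = risk ratio for vitamin C. Allocation is taken as 1:1, as 50 per arm implies.

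**1. Denominator, literal reading.** Trauma cases over all randomised = p × t.

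| p | t = 30% | t = 50% | t = 70% |
|---|---|---|---|
| 10% (assumed) | 3% | 5% | 7% |
| 30% (section 2.2) | 9% | 15% | 21% |

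As counts, with an assumed 100 randomised, 50 trauma patients and 5 trauma cases (Clopper-Pearson 95% intervals):
- whole sample: 5/100 = 5.0% (1.6% to 11.3%)
- trauma patients only: 5/50 = 10.0% (3.3% to 21.8%)

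**2. Denominator, whole-cohort reading.** If elective cases also enter the numerator, the result is t × p + (1 − t) × p_e, where p_e is the elective risk. At p = 10% and t = 50%:
- p_e = 2%: 0.5 × 10% + 0.5 × 2% = 6%
- p_e = 10%: 10%
- p_e = 15%: 12.5%

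This is a coherent proportion, but of a mixed population. It can lie below or above the trauma risk, and the protocol does not say which of the two risks is higher.

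**3. Loss to follow-up, conditional.** If lost patients stay in the denominator, are not imputed and all leave before diagnosis, the figure is p × (1 − d). At p = 10% it is 9.5%, 9% and 8% for 5%, 10% and 20% loss. Restricting to patients with known status avoids this particular shrinkage.

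**4. Pooled arms, conditional.** The figure is p × (1 + RR)/2. At p = 10% it is 6.25%, 7.5% and 8.75% for RR 0.25, 0.5 and 0.75, and 10% for RR 1.

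**5. All together, literal reading.** p × t × (1 − d) × (1 + RR)/2, at p = 10%:
- t = 50%, d = 10%, RR = 0.5: 0.10 × 0.5 × 0.9 × 0.75 = 3.4%
- lowest set tried (30%, 20%, 0.25): 0.10 × 0.3 × 0.8 × 0.625 = 1.5%
- highest set tried (70%, 5%, 0.75): 0.10 × 0.7 × 0.95 × 0.875 = 5.8%

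These combined figures stack assumptions. Only step 1 follows from the sentence itself, given a case mix.

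**The case against.** The strongest reply is that lower limb trauma serves as a label for the whole cohort. The title uses it while the synopsis recruits elective patients, and the first secondary aim is worded for trauma patients but analysed in everyone. On that reading numerator and denominator match. This removes the arithmetic mismatch but not the defect: the result is then the mixed risk of step 2, which fits the synopsis and 2.1 but not the trauma-only objective in 3.1.2 and 3.2.

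Several stronger readings are tempting and should not be made.

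- *Dropouts are counted as CRPS-free.* The protocol does not say so. The inclusion rule in 11.2 concerns treatment received and adherence, and recording an unobserved patient as free of CRPS would sit badly with a ban on imputation. A complete-case proportion is possible, although it would not include all randomised patients. What stands is that the censoring rule is not carried over to this estimate. Losses may not be trivial, since 5.2.6 also withdraws participation from patients it deems non-adherent.
- *Treated patients pull the rate down.* This holds only if vitamin C works, which is the open question. The objective is never defined as untreated incidence. What stands is that the arms are pooled with no estimate for either one.
- *A later trial would be sized on the wrong control rate.* Sections 2.1 and 11.1 look ahead to a larger trial, but no section says this proportion would set its size, and the feasibility outcomes in 3.2 do not include CRPS incidence. That use is an inference.

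The clash between 11.2.1 and the imputation sensitivity analysis is a wording matter and concerns the survival analyses rather than the incidence sentence. Finally, the split by surgery type could be made at analysis without changing trial conduct. That is true, and it is why the correction is cheap.

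**Conclusion.** The point holds as a defect in what the protocol states. The incidence sentence in 11.3 either divides trauma cases by a mixed sample or reports a mixed risk under a trauma label, and the objective differs between the synopsis and 2.1 on one side and 3.1.2, 3.2 and 11.3 on the other. Neither conclusion needs an assumed number.

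The size does need one. On the literal reading the reported figure is the trauma risk times the trauma share, so a true 10% becomes 3% to 7% for shares of 30% to 70%. On the whole-cohort reading the direction is unknown. The effects of loss and of pooling are conditional, and the second vanishes at a risk ratio of 1; it should not be claimed that all three features necessarily bias the figure downward.

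This is a descriptive secondary aim of a feasibility trial, so the matter is worth correcting but does not threaten the primary objective.

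**What to change.** 1. State one incidence population and use it in the synopsis, 2.1, 3.1.2, 3.2 and 11.3.
2. Replace the sentence in 11.3 with: *Cumulative incidence of CRPS at 26 weeks (1 minus Kaplan-Meier, loss to follow-up censored) with 95% CI, reported separately for trauma and elective patients, each with its own denominator, and by arm; the placebo arm gives the incidence without vitamin C.*
3. Limit the no-imputation statement in 11.2.1 to the main analysis, so that it agrees with the sensitivity analysis in 11.3.

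The cost is a few lines of text. Surgery type is already collected (Description of procedures), visits are already scheduled, and 11.3 already treats diagnosis as time-to-event data. The real downside is precision. If half the sample is trauma, the placebo trauma group has about 50 × 0.5 = 25 patients, and 5/25 = 20% has a Clopper-Pearson 95% interval of about 7% to 41%. The report should show that width, and should not treat such an estimate as a firm basis for planning.

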## 12 ETHICS AND DISSEMINATION

### 12.1 Research Ethics Approval & Local Governance Authorisation

This protocol and the informed consent document and any subsequent amendments will be reviewed and approved by the human research ethics committee (HREC) prior to commencing the research. A letter of protocol approval by HREC will be obtained prior to the

---

commencement of the trial, as well as approval for other trial documents requiring HREC review.

Each participating institution will also obtain institutional governance authorisation for the research and associated HREC-approved documents. A letter of authorisation will be obtained from the RGO prior to the commencement of the research at that institution. Institutional governance authorisation for any subsequent HREC-approved amendments will be obtained prior to implementation at each site.

